9.8. End of Study Definition

Patients are followed up when in hospital daily until day 28, death or discharge (whichever occurs sooner). If patients remain in hospital beyond day 28, their electronic records will be periodically reviewed remotely until discharge to enable collection of any outstanding endpoint data. End of study is at 12 months after completion of EQ5D (adults) or PedsQL (paediatrics) patient questionnaire.

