6.3. Secondary Outcomes

For both adult and paediatric populations the outcome measures will be:

- 28-day mortality
- · Ventilator free days
- Length of hospital and critical care stay
- · Thrombotic events
- Requirement for organ support (artificial ventilation, renal replacement therapy, inotropic support)
- Infection organ specific and each episode detailed
- Transfer destination at discharge e.g. home, other medical facility, rehabilitation unit
- Quality of Life at 28 days and 1 year (EQ5D questionnaire and extended Glasgow Outcome Scale for adults, age appropriate PedsQL for paediatric patients)

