8. STUDY DESIGN

ACIT II is a prospective cohort multicentre observational study. It will follow the clinical course of trauma patients from injury in the prehospital phase of care and/or at admission to the emergency department and for the first 28 days. Blood samples and, in some patients, muscle biopsies will be analysed for markers of activation of the coagulation and inflammatory systems. These biomarkers will be correlated with patient injury patterns, trauma-induced physiological disturbances and subsequent clinical course and outcome.

8.1.ACIT SWIFT

ACIT-SWIFT is a sub-study of the primary ACIT study to enable a wider patient recruitment nationwide, and pool resources that are being utilized to deliver the a national trial called SWiFT which will recruit bleeding trauma patients in the prehospital phase of care. Patients enrolled into SWiFT are a specific patient subgroup (major trauma haemorrhage) of interest for the primary ACIT study and hence samples and data will be directly relevant for the general aims and hypotheses. ACIT SWIFT will specifically help to understand the treatment effect of whole blood transfusion after injury through a single blood sample taken on admission (post-dosing of the SWIFT intervention) in combination with data collected as part of the SWIFT trial – for ACIT SWIFT sub study details and paperwork please refer to appendix 4

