9.4.4 Additional data collection

Patient demographics, mechanism of injury, injury type and severity, transfusion of blood products and admission physiology will be recorded in real-time in the emergency department and operating theatre. Patients will then be followed up on a daily basis for organ dysfunction scoring, presence of infection, development of thrombotic events, surgical episodes and other adverse events until Day 28, discharge or death. All of this data (aside from organ dysfunction scores outside of the critical care unit) is routinely collected in the management of injured trauma patients. No additional monitoring or interventions will be required.

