9.4.5 Patient questionnaires

Quality of life assessment will be measured by the use of self reported EuroQol EQ-5D questionnaire and the Extended Glasgow Outcomes Scale (GOS-E) in adults at hospital discharge or Day 28 (whichever is sooner) and again at one year following injury (see Section 9.6 for follow up data collection). In paediatric patients, quality of life will be measured using the Paediatric Quality of Life Inventory (PedsQL) questionnaire that corresponds with the age of the child at the time of injury. Assessment will be carried out at the same time points as for ACIT Protocol V8 16.07.2024

adults. Health economic implications of massive transfusion and resource use will be collected with an additional questionnaire at the one year follow up.

The in-hospital questionnaire will be conducted by research staff with the patient where possible, but may also be completed with the patient's personal consultee if necessary. The questionnaire can be completed in less than five minutes.

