9.6 Follow-up procedures

The 12-month EuroQol EQ-5D (adults) or PedsQL (paediatrics) patient questionnaire will be posted or emailed to surviving patients along with a return stamped addressed envelope. The questionnaire provides instructions for completion of the whole questionnaire, which will take approximately five minutes. Patients who have not returned the questionnaire within two weeks of the initial request will be telephoned as a reminder to complete the questionnaire and may be asked to complete it over the phone if necessary. A maximum of three recorded contact attempts will be made via phone and if these are unsuccessful, no further contact will be made and responses will be marked as not returned. Confirmation with the GP and scrutiny of the hospital care record system will ensure only those patients alive at 12 months receive a questionnaire.

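### 28-day mortality is a secondary outcome, but no step in the protocol records day-28 vital status or date of death for patients who leave hospital earlier

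*Protocol*

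**What the plan says.** Section 6.3 lists "28-day mortality" among the secondary outcomes for adults and children. Section 8 says the clinical course is followed from the prehospital phase and/or "at admission to the emergency department and for the first 28 days", with no mention of stopping at discharge.

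The sections that govern collection are narrower. Section 9.4.4 runs daily follow-up "until Day 28, discharge or death". Section 9.8 states: "Patients are followed up when in hospital daily until day 28, death or discharge (whichever occurs sooner"). It adds one extension: "If patients remain in hospital beyond day 28, their electronic records will be periodically reviewed remotely until discharge". Section 9.4.5 places the first quality-of-life assessment "at hospital discharge or Day 28 (whichever is sooner) and again at one year following injury".

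After discharge, the only reference to survival is in section 9.6 (Follow-up procedures): "Confirmation with the GP and scrutiny of the hospital care record system will ensure only those patients alive at 12 months receive a questionnaire". The schedule in section 9.3 lists no vital-status item.

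**The concern.** A mortality outcome with a fixed horizon needs each patient's status at that horizon, or a date of death from which to derive it. Here the outcome is defined at day 28, while the written collection ends at discharge for anyone who leaves before then.

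The affected group is unlikely to be small. Section 7.2 expects about 55% moderate and 7% minor injuries. Section 11.1 provides for consent being missed because of early discharge. The discharge destinations in section 6.3 include other medical facilities and rehabilitation units, so some patients who count as discharged are still under care. Section 7.1 has other centres recruiting under their own local governance, so discharge and transfer practice may differ between sites. If deaths after discharge are not captured, the shortfall would then differ by site too. That matters for a cohort meant to relate biomarkers to outcome across centres.

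This cannot be left to a statistical analysis plan: no analysis can recover a date of death that was not collected.

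**Working it through.** The protocol gives no mortality rate, discharge rate or sample-size figure for this outcome, so there is no stated figure to reproduce. The check is to follow patients through the written rules and see whether day-28 status can be obtained.

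**Tracing the rules**

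- *Dies in hospital by day 28.* Daily follow-up ends at death (9.4.4, 9.8). Status is known.
- *Still in hospital at day 28.* Daily follow-up reaches day 28, and records are then reviewed until discharge (9.8). Status is known.
- *Discharged or transferred alive before day 28.* Daily follow-up ends at discharge. The remote review does not apply, because it is limited to patients who stay beyond day 28. The questionnaire falls at discharge, that being the sooner date (9.4.5), so there is no day-28 contact. The next event is the 12-month check (9.6).

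**What the 12-month check can supply**

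- Found alive at 12 months: the patient was alive at day 28, so the outcome is settled, provided the result is recorded and used.
- Found dead at 12 months: a death on day 20 cannot be told from one in month 10 without a date, and section 9.6 does not mention recording one.

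So day-28 status for the third group depends on a check whose stated purpose is to decide who receives a questionnaire. Two things are missing: a recorded date of death, and a statement that the check feeds the mortality outcome.

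**Scale, under assumptions**

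Inputs: enrolment of 5,000 (section 7). Assumed, not in the protocol: 75% discharged alive before day 28; 0.5%, 1% or 2% of these dying between discharge and day 28; and the 12-month check recovering none of these deaths.

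Deaths after discharge = 5,000 × proportion discharged × proportion then dying:

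- 0.5%: 0.75 × 0.005 = 0.375 percentage points; × 5,000 = 18.75, about 19 deaths
- 1%: 0.75 × 0.01 = 0.75 points; × 5,000 = 37.5, about 38 deaths
- 2%: 0.75 × 0.02 = 1.5 points; × 5,000 = 75 deaths

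If the proportion discharged is varied from 70% to 90%, the extremes are 0.70 × 0.005 × 5,000 = 17.5 (about 18) and 0.90 × 0.02 × 5,000 = 90 deaths, or about 0.4 to 1.8 points.

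With in-hospital mortality also assumed, at 8%, the share of 28-day deaths falling after discharge would be 0.375/8.375 = 4.5%, 0.75/8.75 = 8.6% or 1.5/9.5 = 15.8%.

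**The case against.** The strongest reply is that section 9.8 qualifies its rule: the daily review applies to patients in hospital, and study follow-up itself runs to 12 months. Section 9.6 has survival checked with the GP and the hospital record, so a death soon after discharge would normally surface. This stands, and it rules out the stronger reading a reader might infer, that these deaths are lost and the reported figure will certainly be in-hospital mortality. What the reply does not supply is a recorded date of death or a link from the check to the outcome.

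A reader might also infer that patients discharged early will be counted as alive at day 28. The protocol does not say so. How unknown status is handled may be set in an analysis plan that is not shown.

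A third inference is that infections and thrombotic events are cut off in contradiction of the outcome list. Section 9.4.4 does stop their collection at day 28, discharge or death, but section 6.3 gives them no 28-day horizon. In-hospital capture of these events is a stated design choice and contradicts nothing.

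Finally, this is one secondary outcome in a cohort without a power calculation (section 10). The primary outcomes in section 6.2 are 24-hour transfusion and organ injury with MODS, so no sample size or primary conclusion rests on it. That is a fair reason to keep the rating moderate.

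**Conclusion.** The concern holds in limited form. The outcome in section 6.3 and the follow-up described in section 8 do not match the collection rules in sections 9.4.4 and 9.8, and no step fixes day-28 status or date of death for patients who leave earlier. Followed as written, the protocol delivers in-hospital mortality to day 28 unless the 12-month check is also used for this outcome.

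The size cannot be derived from the protocol. The figure of about 19-75 deaths in 5,000 (0.4-1.5 points) is an upper limit under the stated assumptions. It shrinks with every death the 12-month check recovers, and reaches zero if the check is complete, dated and used. Any effect on biomarker associations or on pooling across sites is plausible but has not been quantified. Importance is moderate.

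**What to change.** - At the GP and hospital-record check already planned in section 9.6, record vital status and, where the patient has died, the date of death, for every patient discharged or transferred alive. Derive day-28 status from it and say so in section 6.3.
- Report status that cannot be confirmed as unknown, by site, with a sensitivity range for the mortality estimate. Do not censor these patients at discharge. Discharge is related to prognosis, and censoring would assume that those well enough to leave carry the same risk as those who stay, which would push estimated mortality up.
- If this is not done, rename the outcome in-hospital mortality to day 28.
- In either case reconcile sections 6.3, 8, 9.4.4 and 9.8 so that the horizon and the stopping rule agree, and add a vital-status row to the schedule in section 9.3.

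The cost is one CRF field, a few changes of wording, and a small amount of look-up work at a check that already takes place.

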10 STATISTICAL CONSIDERATIONS

Because of the nature of the ACIT II study and its various aims, a power calculation is not applicable.

11 ETHICS

This study will be carried out in accordance with the ethical Principals in the Research Governance Framework for Health and Social Care, Second Edition, 2005 and its subsequent amendments as applicable and applicable legal and regulatory requirements. The study has

been reviewed and approved by the Research Ethics Committee: London – City and East (07/Q0603/29).

11.1 Informed Consent

Our standard operating procedure for obtaining consent is included in Appendix 2. All participants will be enrolled in the study with a waiver of consent due to the emergency nature of the study. Several approaches to obtaining consent will then be used following hospital admission, depending on the mental capacity of the patient and availability of Personal Consultees (relative or friend).

- [1] If a patient is considered to have mental capacity they will be approached directly, and their informed consent requested.
- [2] For patients who lack capacity and where it is not possible to take agreement from a Personal Consultee we will use approaches consistent with the Mental Capacity (England) Act (2005), as below:
- [a] If the patient has capacity, they will be approached.
- [b] If the patient lacks capacity and a personal consultee not available (which is anticipated to be the case in the majority of instances) an independent clinician acting as a professional consultee will be approached within 24hrs of study enrolment to provide consent for the patient to continue in the study. This will usually be a substantive consultant in emergency medicine acting as trauma team leader. The clinician must not be a named local PI or local individual directly involved in the research project and must be of consultant or senior emergency medicine registrar status. In all cases they must have received prior information about the research to enable them to provide advice regarding inclusion in the emergency situation and be included on a log of professional consultees. It is anticipated that this individual will be best placed to advise as they will be aware of the patient's condition and will be the clinician in charge of the immediate clinical care of the patient. Where the trauma team leader is connected with the research project, or unavailable e.g. due to other clinical demands, it is acceptable to ask the opinion of another emergency or trauma physician who is not connected with the research.

- [c] When entry to the study is based on the consent of a doctor who is not connected with the research project (professional consultee), the personal consultee will be approached at the earliest opportunity for agreement to remain in the trial. If the Personal Consultee does not agree to the patient remaining in the trial for further blood tests and data collection to day 28, the research team will clarify whether samples already collected can be retained and where applicable will ask the personal consultee to sign a consent form. All data collected up to the point of withdrawal will be retained. In cases where a personal consultee is not available, we will use the consent signed by the professional consultee until the patient regains mental capacity and they will be approached directly for obtaining personal consent (see point [d]). In cases where a personal consultee is available but all our attempts (2 telephone calls and 2 letters) to contact him/her are unsuccessful, the patient will be kept in the trial based on the consent signed by the Trauma Team Leader (professional consultee). All attempts at contact will be recorded.
- [d] All patients who lacked mental capacity at the time of recruitment will be approached for consent to remain in the trial at the earliest opportunity once they regain capacity. It will be made clear during the consent process that any intervention (blood and/or tissue sample collection) has already taken place and that we are asking for their consent for the collection of further samples and data collection. In cases where patient has regained mental capacity but we didn't manage to obtain a personal consent (because of an early hospital discharge) we will make and document all attempts to contact the patient up to a maximum of 2 calls and 2 letters to the registered address. If these attempts are unsuccessful in obtaining written consent, the patient will be kept in the trial based on the consent signed by the professional or personal consultee. Verbal agreement from the patient regarding their agreement to partake in the study will also be documented in medical record.
- [e] If the patient regains capacity but decides they do NOT wish to remain in the trial we will ask the patient to clarify one of the following: [i] they wish to be removed from the trial, decline any further tissue sampling or data collection and wish for all tissue samples already collected to be destroyed in accordance with local hospital policy. A withdrawal form will be completed. [ii] they do not consent to further tissue sampling but consent to the use of tissue samples that have already been collected. Agreement to tissue storage and use for the study will be documented on the consent form. All data collected up to the point of withdrawal will be retained.

- [f] Patients who die during the follow up period or do not regain mental capacity, will be included in the study based on the advice provided by the personal consultee and/or professional consultee. In cases where the subject dies before our attempt to obtain consent from the patient or the personal consultee, the patient will remain in the trial based on the consent obtained by the professional consultee and we will not attempt future telephone contact with relatives/personal consultee in order to minimise stress and anxiety associated with the unexpected and traumatic death of their relative / next of kin.
- [g] In general, the same procedures and principles will apply to the recruitment of paediatric patients with parents or legal guardians providing consent for children aged under 16 years who lack capacity. Paediatric patients who are Gillick competent will give consent for their own involvement. Wherever appropriate children will be involved in the discussion (with parents or legal guardians) regarding consent to use their samples and data. Discretion will be applied by the recruiting member of the research team regarding approaching a parent or legal guardian at all times, particularly during initial screening and recruitment in order to avoid causing undue stress and anxiety. Advice will be taken from the independent clinician in cases of uncertainty. Procedures for paediatric consent are detailed fully in appendix 2.

11.2 Safety Considerations

All parts of the study will be carried out to avoid patient risk and minimize discomfort at all times. At no time will patient care be compromised or delayed for the purposes of the study.

We will record all adverse events associated with the study and review them as they occur, and collectively at monthly intervals. Participation in research may involve some degree of loss of privacy. However this risk will be minimized by our data protection methods and we are not performing any tests that might subsequently result in significant personal, financial or social risk to the research subjects. We will make every effort to ensure that our data is secured and patients' privacy is protected, in accordance with our local information governance guidelines.

11.3 Specific Risks

11.3.1 Blood sampling

The risks of blood sampling are limited to some potential bruising at the site of venepuncture, and discomforts are limited to needle puncture (where no arterial line is already in place).

11.3.2 Muscle Biopsy

The risks associated with performing a muscle biopsy under general anaesthesia are minimal as it will only be taken during a procedure where muscle is already exposed and surgery is being performed on the same anatomical location. There may be a very small amount of bleeding at the site of the biopsy but will be controlled at the time of surgery with conventional surgical practice (e.g. diathermy).

11.4 Benefits to study participants

None

11.5 Potential benefits to society

Trauma remains the leading cause of death in patients between 1 and 45 years of age, and is the fifth most frequent cause of death overall (1). In general, injured patients die either from major haemorrhage, traumatic brain injury or multiple organ failure (2). Patients who die from haemorrhage or brain injury do so within the first few days following injury. For those patients who die after the first 24 hours, 60% will die of multiple organ failure. Those patients with multiple organ failure who do not die have extensive intensive care and hospital stays and are very expensive in terms of cost, resources and personnel (11).

It is clear from several studies that the outcome of trauma patients is determined in the first few hours following injury. However, we currently have very little understanding of the processes at work during this early injury period. We currently have an almost total lack of understanding of the initiation and progression of activation of the coagulation and inflammation systems, and how they lead to multiple organ failure – questions this study is designed to investigate.

Trauma patients tend to be young, active members of society, often with good jobs and young families to support, who are essentially 'cut down in their prime'. However, the growing elderly population now represents a larger and important demographic in trauma since the combination of multisystem injury and age-related comorbidities or low energy and poor physiological reserve produce poor outcomes. We hope that this study will allow us to identify specific points in the genesis of multiple organ failure that may be used to target interventions in the future, and hence reduce this huge burden of death and disability.

11.6 Risk/benefit analysis

Although the study carries no direct benefit to the subjects, the bulk of the study is observational, and interventions that are carried out are routine, carry small or minimal risk, and the study has been designed to reduce discomfort and risks to the study subjects.

12 PUBLIC INVOLVEMENT

The Centre for Trauma Sciences PPI group - Patient & Public Advisors in Injury Research (PAIR) was set up after the ACIT study first started in 2007. However the group are integral to all protocol amendments and revision of patient consent forms and information sheets. All documentation aimed at children recruited to ACIT have also been reviewed by a RLH youth PPI group – the Youth Empowerment Group. Key research findings generated from the ACIT II study are presented at the PAIR meetings with input on how best to disseminate to the lay public.

13 DATA HANDLING AND RECORD KEEPING:

